### 8.2.3 Handling of Replicate Data

A subject having an AE coded to the same preferred term more than once during the study will be counted only once in the incidence calculations for that AE. Similarly, if a subject has more than one AE in a single body system, the incidence will be counted only once for that body system. If a subject has the same AE more than once, the occurrence that is of greatest severity will be used in the calculation of the incidence of individual AE by severity. Similarly, the AE considered most closely related to study drug will be used in the calculation of incidence of individual AE by relationship in case a subject has the same AE more than once.

For the laboratory, vital signs, ECG, EEG and other safety variables datasets, the measurement noted as the scheduled visit measurement will be used in the analysis. If more than one assessment is present at a scheduled visit, then the nearest assessment for evaluation visit (day) will be used in the summaries of the actual values and changes from baseline. In the event of two assessments being equally close to the scheduled visit (day), the last assessment will be used.

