- c: Visit 2 is the Baseline Visit and may be conducted up to 1 week before the first dose of study drug (ie, from Day -7 to Day -1). The Baseline Visit should be at least 2 weeks after the day of Screening Visit Tier 2 assessments. After completion of study assessments subjects who are eligible will be randomized to placebo or E2027. They will be dispensed with study drug before leaving clinic at Visit 2. Visit 3 (Day 1) will be conducted by telephone. On Day 1 the subject will start taking study drug in the morning at home. The site study staff will telephone the subject/caregiver to check that the subject has taken study drug and to elicit any AEs. Subjects who develop acute illnesses which make it inappropriate to start taking study drug may have their Baseline Period extended by 1 week after discussion with the sponsor medical monitor.
- d: Subjects who discontinue study drug prematurely for any reason will undergo an Early Discontinuation (ED) Visit within 7 days of their final dose of study drug. In addition, subjects who prematurely discontinue study drug are expected to continue in the study for the originally scheduled visits, starting with next such visit that is >7 days after the ED Visit. Subjects who prematurely discontinue the study should attend at least 1 originally scheduled visit after the ED Visit.
- e: Unscheduled visits may be conducted at any time as clinically indicated in the judgment of the investigator or as specified in the protocol. Not all assessments indicated under Unscheduled Visits need to be conducted – actual assessments needed will be determined by the investigator or as specified in the protocol and will be based on the specific visit.
- f: At Screening, Tier 2 assessments in subjects should be performed in the following order: MMSE and GDS first; then MoCA and SCOPA-Sleep. The caregivers or informants should complete the SFQ, CFI and NPI. Subjects who do not meet eligibility criteria on MMSE or GDS should be screen failed and the other assessments do not need to be performed. The caregiver or informant must attend in person with the subject. The above assessments should be completed before more invasive procedures (eg, physical examination, ECG, blood draws). Assessments at all other tiers are not required to be performed in any prespecified order.

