#### **5.1.2 Secondary Endpoints**

CGIC-DLB scale at 12 weeks of treatment

- Change from baseline at 12 weeks of treatment in the following endpoints:

- CFI score
- MMSE total score
- NPI total score, subscores and caregiver or informant distress score

Safety and tolerability of E2027 as measured by

- Incidence of adverse events including severe AEs, serious AEs, AEs resulting in discontinuation
- Incidence of orthostatic hypotension and orthostatic tachycardia
- Incidence of markedly abnormal laboratory values and shifts from baseline of laboratory values
- Incidence of abnormal ECG parameters and abnormal ECG findings
- Incidence of suicidality based on C-SSRS
- Changes from baseline in the total score of UPDRS-III

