### 8.2.2 Treatment Duration for Safety Analyses

The treatment duration for all safety variables is considered to begin on Day 1 and ends 28 days after the last dose of study medication. Treatment emergent safety data (ie labs, vital signs and ECGs) are defined as observations that were recorded during treatment or within 28 days following the last dose of study drug, these will be flagged in the listings as “off treatment, but treatment emergent”. This data will be windowed and summarized as described below. Data after 28 days of last dose will be flagged as Post TE and listed only.

For summaries of safety by time points, the time points will be relative to date of first dose. For standardized reporting, study day windows relative to the first dose (Day 1) in the study will be applied to determine into which week the data will be mapped. All pretreatment assessments are conducted during Screening/Baseline Periods before Day 1. The Analysis Baseline is the last non-missing pretreatment assessments. Scheduled, unscheduled, and early discontinuation visits will be mapped to weeks. Table 8 below gives the mapping of relative day ranges to week for non-AE safety variables. If a subject did not have a recorded observation falling within a given range of days in order to be assigned to a week, the subject’s data for that week will be regarded as missing for summarization purposes. If there are two or more assessments in the same window, the following rules will be used:

- If the window is for the screening/baseline assessment, then the latest assessment will be used in the summary tables;
- If the window is for the follow-up assessment, then the latest assessment will be used in the summary tables;
- If the window is not for the screening/baseline or the follow-up assessment, then the assessment closest to the scheduled assessment will be used in the summary tables. Note that if two assessments are equidistant from the scheduled assessment then the last assessment of the two (within the allowable window) will be used.

Windowing Period	Study Day Range (Relative to First Dose)	Week
Screening	$(-42) \leq \text{Day} \leq (-8)$	
Baseline	$(-7) \leq \text{Day} \leq (-1)$	

Analysis Baseline	-	a
Treatment	$1 \leq \text{Day} \leq 21$	2
Treatment	$22 \leq \text{Day} \leq 35$	4
Treatment	$36 \leq \text{Day} \leq 53$	6
Treatment	$54 \leq \text{Day} \leq 74$	9
Treatment	$75 \leq \text{Day} \leq 98$	12
End of Treatment (EOT)	-	b
Follow up	Follow up visit	c

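### SAP 8.2.2 and 8.2.3 select safety readings by conflicting rules, and neither exempts the by-subject laboratory, ECG and orthostatic incidence tables

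*SAP*

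**What the plan says.** - **SAP 8.2.3** covers the laboratory, vital-sign, ECG and other safety data sets and says that "the measurement noted as the scheduled visit measurement will be used in the analysis". Its next sentence deals with several assessments at one scheduled visit: "the nearest assessment for evaluation visit (day) will be used in the summaries of the actual values and changes from baseline".
- **SAP 8.2.2** introduces its windows as serving summaries by time point. It says "Scheduled, unscheduled, and early discontinuation visits will be mapped to weeks" and, where a treatment window holds two or more readings, "the assessment closest to the scheduled assessment will be used in the summary tables", with the later one taken in a tie. It defines treatment-emergent safety data as "observations that were recorded during treatment or within 28 days following the last dose of study drug", without restriction to scheduled visits.
- **SAP 5.6.3** defines a treatment-emergent markedly abnormal value (TEMAV) as a post-baseline rise in grade to 2 or more (3 or more for phosphate).
- **SAP 5.6.5** counts subjects who have one or more abnormal QTcF results after baseline in the treatment period. A further table of QTcF, PR and QRS categories has a treatment-period entry as well as entries for each visit week and end of treatment.
- **SAP 5.6.4** tabulates orthostatic hypotension and tachycardia by treatment group and visit.
- **SAP 5.1.2** makes these incidences secondary endpoints, for example "Incidence of abnormal ECG parameters and abnormal ECG findings".
- **Protocol Table 6** marks vital signs, ECG and laboratory tests in the Unscheduled column. Its footnote e says "Unscheduled visits may be conducted at any time as clinically indicated in the judgment of the investigator".

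**The concern.** Choosing one reading per visit is sensible for means and changes by visit. It does not suit a by-subject count of whether an abnormality ever occurred, because the qualifying reading may be the one left out. At least some Unscheduled Visits are made because something looked wrong clinically, so readings taken there cannot be assumed to go missing at random.

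The SAP gives two selection rules that disagree on whether unscheduled readings are eligible at all. It does not say which rule governs the incidence tables, or whether the definitions in Section 5.6 override both. Two programmers working faithfully from this SAP could report different incidences for the same secondary endpoint, and the more literal one would report the lower figure.

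**Working it through.** The plan states no figure to reproduce. The check sets the rules side by side and applies them to the visit schedule.

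**1. The rules compared**

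| Place in SAP | Eligible readings | Readings used | Stated scope |
|---|---|---|---|
| 8.2.3, first sentence | Scheduled visit | The scheduled one | Analysis, no exception |
| 8.2.3, second sentence | Several at one scheduled visit | Nearest | Actual values and changes only |
| 8.2.2 | Scheduled, unscheduled, ED | Nearest in each window | Summary tables, in a paragraph on time points |
| 5.6.3 (TEMAV) | Post-baseline | Not stated | Incidence |
| 5.6.5 (ECG) | Post-baseline, treatment period | Any one abnormal result | By-subject count |
| 5.6.4 (orthostatic) | Postbaseline visits | Not stated | By visit |

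**2. Windows (SAP 8.2.2)**

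- Days 1–21, 22–35, 36–53, 54–74 and 75–98 have widths of 21, 14, 18, 21 and 24 days.
- The total is 21 + 14 + 18 + 21 + 24 = 98 days.

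**3. Laboratory test on Day 30**

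- Table 6 schedules on-treatment laboratory tests only at Weeks 6 and 12.
- Day 30 lies in the Week 4 window (Days 22–35), which has no scheduled draw. Under 8.2.2 the test is normally the only reading there and is kept. Under a literal 8.2.3 it is not a scheduled-visit measurement and is omitted.
- The Week 2, 4 and 9 windows have no scheduled draw, so the rules can part in this way over 21 + 14 + 21 = 56 of the 98 days.

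**4. ECG on Day 46**

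- Visit 6 is Day 42. Days 42 and 46 share the Week 6 window (Days 36–53).
- Distances from the scheduled day are |42 − 42| = 0 and |46 − 42| = 4. Rule 8.2.2 selects Day 42, and so does 8.2.3, because Day 42 is the scheduled visit.
- Take illustrative QTcF values of 455 ms on Day 42 and 515 ms on Day 46. If the selected record feeds the category table, the subject enters only the >450 ms row. If all records feed it, the subject also enters the >480 and >500 ms rows.

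**5. Orthostatic events**

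The tabulation is by visit and no any-time row is specified. An event seen only at an off-target unscheduled reading, in a window that also holds a scheduled reading, appears in no row.

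**6. After Day 98**

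For a last dose on Day 84, treatment-emergent data run to Day 84 + 28 = 112, but the last treatment window closes on Day 98. An unscheduled reading on Days 99–112 is treatment-emergent and has no treatment week.

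**7. Size**

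The documents give no rate of Unscheduled Visits or of abnormal readings at them, so no expected effect can be calculated. If all 91 planned subjects in an arm enter the Safety Analysis Set, each subject lost from a count moves that arm's incidence by 1/91 = 1.1 percentage points.

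**The case against.** The case for leaving the text alone is substantial.

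- The windowing paragraph in 8.2.2 is framed around time points, and the nearest-reading sentence in 8.2.3 is confined to actual values and changes. Both can be read as by-visit rules already.
- The definitions in 5.6.3 and 5.6.5 are specific and can be read as covering every post-baseline value. The treatment-period entry in 5.6.5 is separate from the weekly ones.
- The readings that matter most have a second route. Exclusion Criterion 15 bars a QTcF above 450 ms, so 515 ms is a rise of at least 515 − 450 = 65 ms. Protocol 9.5.1.5.1 makes a QTcF above 450 ms with a rise of more than 60 ms an adverse event, and Protocol 9.5.5 lists QTcF above 500 ms as a reason for discontinuation. Laboratory abnormalities that lead to intervention, and orthostatic hypotension that is symptomatic or needs intervention, are also adverse events.

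The third point stands and limits the consequence. The first two give a plausible intention, but the opening sentence of 8.2.3 refers to the analysis without qualification, 8.2.2 refers to summary tables in general, and no precedence is stated. The by-visit reading also does not help orthostatic events, which have only a by-visit table.

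A reader might go further in ways that the documents do not support:

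- **That unscheduled laboratory draws supply a large share of TEMAVs, or that unscheduled readings are the most abnormal.** No rates are given, and footnote e also allows visits specified in the protocol, such as efficacy assessments before a medication change.
- **That unscheduled readings cannot reach the end-of-treatment row.** Note b to the safety windows admits the last value within 7 days of the last dose when the Week 12 or ED visit is missing.
- **That only the laboratory low/normal/high shift tables use extreme values, or that C-SSRS is affected in the same way.** SAP 5.6.6.1 already uses the maximum ideation rating and reports suicidality at any point in the study.

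**Conclusion.** The point holds as a conflict between stated rules that can change reported secondary safety incidences. It is clearest for unscheduled laboratory draws in weeks with no scheduled draw, where 8.2.2 and 8.2.3 give opposite answers, and for orthostatic events. For ECG categories the loss occurs only if a selection rule is allowed to override the wording of 5.6.5.

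It would be too strong to infer that the SAP has a settled scheduled-only policy. Section 8.2.2 expressly brings in unscheduled and ED readings, and 5.6 can be read to use them all.

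Any error is towards understatement in the numerical tables. Its size, and whether it differs between arms, cannot be derived from the documents. The conclusion assumes that some clinically prompted readings occur between visits. It does not touch the efficacy analyses, and the adverse event tables are not affected by these rules for measured values. The text should be settled before unblinding, because afterwards the choice of records could be made with knowledge of its effect.

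**What to change.** 1. In SAP 8.2.2 and 8.2.3, state one rule: a single reading per window is used only for by-visit descriptive statistics, by-visit rows and by-visit shift tables. Make unscheduled and ED readings eligible for it in both sections.
2. State that by-subject any-time incidence tables use all treatment-emergent post-baseline readings, including scheduled, unscheduled, repeat and ED. Name the tables: TEMAV; QTcF, PR and QRS categories; orthostatic hypotension and tachycardia; clinically notable vital signs.
3. In SAP 5.6.4, add an any-time row for each orthostatic event beside the by-visit rows.

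C-SSRS needs no change. The second statement also covers readings after Day 98 that are still treatment-emergent.

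The cost is a few sentences and a record-selection flag in the programs. The downside is that incidences may be slightly higher in both arms.

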### Handling of prior/concomitant medication

If the subject has taken the same concomitant medication (as coded to preferred WHO-drug term) more than once, the subject will be counted only once in the tabulation.

### 8.2.4 Safety Data Collected After the ED Visit

No post TE data (data collected beyond treatment emergent window) will be summarized separately for safety summaries. If data is within the treatment emergent period, they will be windowed into the visits as above. Data that is not treatment emergent will be flagged in the listings.

## 8.3 Algorithms for Efficacy Parameters

This section describes the algorithms and missing data handling procedure to derive the totals scores for the efficacy parameters MoCA, NPI, MMSE, CFI, and SCOPA-Sleep.

### Montreal Cognitive Assessment (MoCA)

This scale assesses different cognitive domains: attention and concentration, executive functions, memory, language, visuoconstructional skills, conceptual thinking, calculations, and orientation. It is reported to be useful to characterize global cognitive impairment in DLB. The MoCA scale is composed of 11 assessments. The following are the assessments and possible points earned for each assessment:

Visuoconstructional skills (0 – 5 points), Naming (0 – 3 points), Memory (No points), Attention: Forward/backward digit span (0 – 2 points), Attention: Vigilance (0 – 1 point), Attention: Serial 7s (0 - 3 points), Language: Sentence repetition (0 – 2 points), Language: Verbal fluency (0 – 1 points), Abstraction (0 – 2 points), Delayed recall (0 – 5 points), and Orientation (0 – 6 points).

The MoCA Total Score (range 0 to 30) = sum of all points earned. If any assessment is missing then the Total Score is missing. The lower the total score, the worse the cognitive impairment.

### Clinician's Interview Based Impression of Change Plus Caregiver Input (CIBIC-Plus)

This scale is designed to measure various domains that describe subject function: general, mental/cognitive state, behavior, and activities of daily living. The CIBIC-Plus scores will be assigned by clinicians and the possible scores are: 1 (marked improvement), 2 (moderate improvement), 3 (minimal improvement), 4 (no change), 5 (minimal worsening), 6 (moderate worsening) and 7 (marked worsening).

### Neuropsychiatric Inventory (NPI)

This scale assesses frequency and severity of 12 neuropsychiatric symptoms commonly described in dementia patients: delusions, hallucinations, agitation/aggression, depression/dysphoria, anxiety, elation/euphoria, apathy/indifference, disinhibition, irritability/lability, motor disturbance, nighttime behaviors and appetite/eating changes. The scale is composed of 12 items, each item score ranges from 0 to 12.

The NPI Total Score (range 0 to 144) = sum of all item scores. If any item score is missing then the Total Score is missing. The higher the total score, the more severe the symptoms.

A subscore covering the domains of delusions, hallucinations, apathy and depression (NPI-4) will also be derived. The subscore (0 to 48) = sum of 4 corresponding item scores. If any one of the 4 item scores is missing then the subscore is missing.

The caregiver distress (NPI-D) is rated by caregiver based on his or her own stress on a five point scale from 0 - no distress, 1- minimal, 2 - mild, 3 - moderate, 4 - moderately severe, 5 - very severe or extreme.

NPI-10 is the subscore (0-120) of all items except night-time behavior and appetite/eating changes. If any one of the 10 item scores are missing then the subscore is missing.

### Mini-Mental State Examination (MMSE)

The MMSE is composed of 30 questions group into domains, see Table 9. For each of the MMSE domains add the correct responses. If a domain has missing data then the domain is missing. From the domains compute the six items as show in Table 9. If any domain is missing then the item is missing. The MMSE Total Score (range 0 to 30) = sum of the six items. If any item score is missing then the Total Score is missing. The lower the total score, the worse the impairment.

**Table 9 MMSE Domains and Items**

Domain	Score Range	Item	Score Range
1. Orientation to Time	0 to 5	1. Orientation to Time	0 to 5
2. Orientation to Place	0 to 5	2. Orientation to Place	0 to 5
3. Registration	0 to 3	3. Registration	0 to 3
4. Attention and Calculation a	0 to 5	4. Attention and Calculation	0 to 5
5. Recall	0 to 3	5. Recall	0 to 3
6. Naming	0 to 2	6. Language (Sum of Naming, Repetition, Comprehension, Reading, Writing, and Drawing)	0 to 9

7. Repetition	0 to 1		
8. Comprehension	0 to 3		
9. Reading	0 to 1		
10. Writing	0 to 1		
11. Drawing	0 to 1		
		Total Score	0 to 30

### Cognitive Fluctuation Inventory (CFI)

This scale assesses cognitive fluctuation with the same format as the NPI. It evaluates fluctuation in various domains including attention, ability to perform daily functions, orientation, verbal communication and behaviour. It is scored based on frequency and severity with a score range of 0–12. The scale also assesses the degree of caregiver/informant distress engendered by the symptoms.

### Scales for Outcome in Parkinson's disease—Sleep (SCOPA-Sleep)

There are sections for night time and daytime sleep. There are 5 questions for night time sleep: (1) trouble falling asleep, (2) awakening during the night, (3) episodes lying awake too long at night, (4) early morning waking and (5) patient's impression whether they had adequate duration of sleep at night. There are 6 questions for daytime sleep, (1) falling asleep unexpectedly during the day or evening, (2) falling asleep while sitting peacefully, (3) while watching television or reading, (4) while talking to someone, (5) trouble staying awake during the day or evening, and (6) experiencing falling asleep as a problem.

## **8.4 Algorithms for Safety Parameters**

UPDRS-III subscores are defined as follows:

Tremor: sum of MDS-UPDRS-III category 3.15 to 3.18 (sum of 10 items from 4 categories: 3.15 Postural Tremor of the Hands, 3.16 Kinetic Tremor of the Hands, 3.17 Rest Tremor Amplitude, 3.18 Constancy of Rest Tremor).

Rigidity: sum of MDS-UPDRS-III category 3.3 (sum of 5 items from 1 category: 3.3 Rigidity).

Bradykinesia: sum of category 3.4 to 3.8 and 3.14 (sum of 11 items from 6 categories: 3.4 Finger Tapping, 3.5 Hand Movements, 3.6 Pronation-Supination Movements of Hands, 3.7 Toe Tapping, 3.8 Leg Agility, 3.14 Global Spontaneity of Movement [Body Bradykinesia]).

Postural instability and gait difficulty (PIGD): sum of category 3.9 to 3.13 (sum of 5 items from 5 categories: 3.9 Arising from Chair, 3.10 Gait, 3.11 Freezing of Gait, 3.12 Postural Stability, 3.13 Posture).

DEMQOL subscores are defined as follows:

Daily activities contains items 20 to 28, memory contains items 14 to 19, negative emotion contains items 2, 4, 7, 8, 9, 11, 12 and 13 and positive emotion contains items 1, 3, 5, 6, and 10.

DEMQOL-Proxy subscores are defined as follows:

Daily activities contains items 21 to 31, memory contains items 12 to 20, negative emotion contains items 2, 3, 5, 7, 9 and 10 and positive emotion contains items 1, 4, 6, 8, and 11.

## **9 PROGRAMMING SPECIFICATIONS**

The rules for programming derivations and dataset specifications are provided in separate documents.

## **10 STATISTICAL SOFTWARE**

All statistical analyses will be performed by Eisai Inc., using SAS Version 9.4 or later.

## **11 MOCK TABLES, LISTINGS AND GRAPHS (TLGS)**

The study TLG shells will be provided in a separate document, which will show the content and format of all tables, listings, and graphs in detail.

## 13 APPENDICES

### 13.1 Sponsor's Grading for Determining Markedly Abnormal Laboratory Results

The following table of Sponsor's Grading for Laboratory Values is copied from the protocol, Appendix 2.

